## 2.2.4 Tolerability

Tolerability of treatment will be summarized and compared descriptively between treatment groups in terms of:

- Duration of Exposure
- Device usage data will be available from the devices permitting a treatment response analysis.
- Mentor support group usage (hours per week)

## 2.2.5 Blinding Assessment

In order to ensure the randomization of subjects to blinded treatment has been effective, a blinding assessment will be performed as part of the final analysis.

Subjects will be asked at baseline, 1 and 6 months to state which treatment arm they think they have been assigned to. Post unblinding of treatment at the final analysis, the true randomization list will be compared with the subject responses.

## 2.3 Statistical Hypothesis

## 2.3.1 Primary

As the primary efficacy endpoints differ between regulatory clearance pathways, the corresponding statistical hypotheses, tested at 6 months, are also specific to the regulatory pathway.

For both the *USA and EU regulatory clearance pathways*, there will be one statistical hypothesis test to determine the efficacy of the VeSTAL device in comparison to the sham control:

There is no significant difference between the mean percentage weight loss of participants using the VeSTAL device and the sham control, i.e.  $\bar{x}_v - \bar{x}_s >= 0$ , where  $\bar{x}_v$  and  $\bar{x}_s$  are the mean percentage weight loss of participants using the VeSTAL device and sham control respectively.

For the purpose of the *USA regulatory clearance pathway*, the study will be deemed to have met the efficacy criteria if this hypothesis is rejected, and two numerical criteria are achieved:

- The difference between the mean percentage weight loss of participants using the VeSTAL device and the sham control is at least 2% as observed from the confidence intervals, (i.e. equivalent to assessing the hypothesis  $\bar{x}_v \bar{x}_s >= 2$ ).
- The lower bound of the 95% confidence interval of the response rate in the VeSTAL device group exceeds 50%, with response defined as a loss of at least 5% of body weight i.e.  $p_v \frac{1}{2} \left( C_u C_L \right) \geq 50\%$ , where  $p_v$  is the proportion of participants who lose at least 5% body weight using the VeSTAL device.  $C_L$  and  $C_U$  are the lower and upper bounds of the 95% confidence interval.

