## Study Acceptance Criteria USA:

- Mean: There should be at least a 2% total body weight loss (TBWL) superiority margin between the active-product and sham-treated groups.
- Categorical: The proportion of participants who lose 5% TBWL or more in the active-product group is at least 50%, independent of the sham control

Both weight loss efficacy acceptance criteria must be met to claim success. These criteria can be specified in mathematical formulae as follows:

Rejection of both the null hypotheses  $\mu A - \mu C \le 2\%$  and  $\pi A \le 50\%$  at the 2.5% (1-sided) level Where:

 $\mu$ A and  $\mu$ C are the underlying population mean percentage weight loss on active and control respectively

 $\pi A$  is the underlying population proportion of subjects who lose  $\geq 5\%$  of baseline body weight on active.

Vestibular Stimulation to Trigger Adip Clinical Trial Project Name	68 of 112		
Clinical Protocol for VeS			
243973(NI)_181094(UCSD USA)	11		
Study Reference Number	Document Type	Document Number	Revision Number

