#### **Neurovalens Limited**

Identifier: EXP18020

Clinical Study Identifier: 243973

Percentage weight loss at any nominal time will be calculated as the percentage difference between the weight measurements recorded at baseline, minus the respective time point's weight measurement per subject. Response rate at any time will be calculated as the proportion of subjects who lose at least 5% body weight, with percentage weight loss defined as above.

Similarly, percentage change at any nominal time for other variables will be calculated as the percentage difference between the measurements recorded at baseline, minus the respective time point's measurement per subject.

Prior to performing statistical comparisons, the continuous efficacy endpoints will be evaluated for conformance to parametric assumptions, for example by assessing their distribution, and may be transformed e.g. log transformed if appropriate. If the parametric assumptions cannot be met through transformation, a non-parametric alternative may be used instead.

The laboratory and vital signs data will be recorded using the USA units at each site. As a result, it is not expected that any conversions will be required to standardise data into consistent units.

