## 12.1.1 Primary Efficacy Analyses

As the primary efficacy endpoints differ between regulatory clearance pathways, the primary efficacy analyses also differ accordingly.

For both the *EU and USA regulatory clearance pathways*, the primary efficacy endpoint will be summarized using summary statistics for the percentage weight loss at the 6 month time point. The mean percentage weight loss will also be presented graphically, by treatment group, over time. Summaries and graphical outputs will be produced for observed data unless specified otherwise..

For the continuous efficacy endpoint, mean percentage weight loss at 6 months, the difference between treatment groups will be assessed using a linear model controlling for covariates of interest: gender and baseline weight. The least square (LS) mean difference between groups will be assessed for a statistically significantly difference from 0 i.e. p-value <0.05. For the USA regulatory clearance pathway, the lower limit of the confidence interval of the LS Mean difference between groups will be assessed against the 2% target for a successful study, whereas the EU regulatory clearance pathway will assess whether the LS mean difference between groups is significantly different from zero. Analysis using multiple imputation for missing data will be primary, with the LOCF and BOCF imputation methods used for supportive analyses.

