### 12.1.2 Supportive Primary Efficacy Analyses

For the purposes of the *USA regulatory clearance pathway*, the number and percentage of people achieving a loss of at least 5% of their body weight by the 6 month time point in the VeSTAL device treatment group will be presented with a two-sided 95% exact binomial confidence interval for the response rate. The criterion for success is that the lower bound of the 95% confidence interval of the response rate in the VeSTAL device group exceeds 50%. The analysis will use the multiple imputation for missing data as primary, with the LOCF and BOCF imputation methods as supportive.

A Fisher's exact test will also be used to compare the response rates in each treatment group and to detect whether the difference between groups is statistically significant. This will be repeated using multiple imputation, LOCF and BOCF methods for missing data. For the multiple imputation-based analysis, the median p-value approach will be used to generate the Fisher's exact test p-value (Eekhout 2017) and the exact confidence intervals described above will be produced using the imputation with a p-value equal to or nearest the median p-value.

In addition, a sensitivity analysis will be performed with the binary weight loss endpoint, to assess the impact of imputing the best and worst case scenarios for the binary response, when the total body weight loss at 6 months is missing. As per section 10.2, a tipping point analysis will also be utilised to demonstrate the level of imputation which changes the significance of the binary weight loss criterion.

No supportive primary efficacy analyses are required for the *EU regulatory clearance pathway*.

Identifier: EXP18020 Clinical Study Identifier: 243973

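### SAP 2.3.1 writes the primary null in the wrong direction and glosses the responder rule with a half-width formula that can pass one responder too few; SAP 12.1.1 and 12.1.2 state workable rules, so 2.3.1 should be brought into line.

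*SAP*

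**What the plan says.** SAP 2.3.1 sets one hypothesis for both pathways: "There is no significant difference between the mean percentage weight loss of participants using the VeSTAL device and the sham control". An i.e. clause then writes it as x_v - x_s >= 0, in sample means. For the USA, "the study will be deemed to have met the efficacy criteria if this hypothesis is rejected" and two numerical criteria are also met; for the EU, the same rejection is needed plus an observed difference of at least 2%. SAP 10.1 fixes the sign of the endpoint: percentage loss is formed from the "weight measurements recorded at baseline, minus the respective time point" value, so a positive difference favours the device.

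The first US criterion, a difference of at least 2% judged from the confidence interval, is said to be equivalent to assessing x_v - x_s >= 2. The second reads "The lower bound of the 95% confidence interval of the response rate in the VeSTAL device group exceeds 50" (per cent), followed by an i.e. formula: p_v minus half of (C_U - C_L), at or above 50%.

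Other sections differ:

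- **Protocol 18.1 (USA):** the nulls to reject are muA - muC <= 2% and piA <= 50%, "at the 2.5% (1-sided) level", and "Both weight loss efficacy acceptance criteria must be met to claim success".
- **Protocol 18.2 (EU):** H0 is muA = muC, two-sided.
- **SAP 12.1.1:** the LS mean difference is tested two-sided against 0; for the USA its lower confidence limit "will be assessed against the 2% target for a successful study".
- **SAP 12.1.2:** the response rate is "presented with a two-sided 95% exact binomial confidence interval for the response rate", and success requires the lower bound to be above 50%.

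**The concern.** SAP 2.3.1 is where the US criteria are combined into a single success rule, and its symbols do not say what its words say.

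The mean hypothesis points the wrong way as the statement to be rejected, and the 2% expression is an alternative presented as a hypothesis to assess. The responder criterion has two definitions in one bullet, and they are not equivalent once the interval is the exact one. Because both US criteria must be met, one responder can decide the US claim, and a plan that offers two pass marks leaves a choice open after unblinding.

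Readers cannot simply fall back on the protocol: SAP 13 says the SAP supersedes the protocol's analyses (it cites protocol version 5). SAP 1 also records that the team running the analysis is not the one that wrote the SAP version agreed with FDA.

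**Working it through.** **Direction of the mean hypothesis**

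- Loss = baseline minus follow-up (SAP 10.1), so device better than sham means x_v - x_s > 0.
- Rejecting x_v - x_s >= 0 supports x_v - x_s < 0: the device group lost less weight.
- This conflicts with the hypothesis's own words (no difference), with SAP 12.1.1 (two-sided against 0), with protocol 18.1 and 18.2, and with the eight secondary nulls in SAP 2.3.2, all written as = 0.
- The US margin null in protocol 18.1 is muA - muC <= 2%. The SAP's >= 2 is what the trial hopes to show.

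**Responder rule: inputs**

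- Sample size (SAP 5): 180 with 10% dropout gives 180 / 0.90 = 200, which reproduces the plan's figure. At 1:1 this is 100 active.
- Denominator (SAP 7): ITT, all randomized, so n = 100.
- Interval (SAP 12.1.2): two-sided 95% exact binomial (Clopper-Pearson).
- The minus signs in the formula are missing from the available text. Subtraction is the only sensible reading, and their absence is not counted as an error.

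**Why the two rules differ**

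p_v - 1/2(C_U - C_L) = C_L + [p_v - 1/2(C_U + C_L)]

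The formula equals C_L only if p_v is the midpoint of the interval. Above 50% the exact interval is pulled towards 50%, so the bracket is positive and the formula exceeds the true lower limit.

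**Results at n = 100**

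- **59 responders:** the formula gives 48.99%. Fails under both rules.
- **60 responders:** exact interval 49.72% to 69.67%. Half-width = (69.67 - 49.72)/2 = 9.975 points, so the formula gives 60 - 9.975 = 50.025, or 50.03% from unrounded limits: pass. The exact bound of 49.72% fails.
- **61 responders:** exact interval 50.73% to 70.60%. Passes under both rules.

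One-sided error at a true rate of 50%:

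- Formula: P(X >= 60 | 100, 0.5) = 0.0284, above 0.025.
- Exact bound: P(X >= 61 | 100, 0.5) = 0.0176.

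**Other arm sizes, n = 80 to 120**

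- The pass marks differ at 13 of 41 sizes: 80, 85, 87, 89, 96, 98, 100, 105, 107, 109, 116, 118 and 120.
- At each of these the formula needs one responder fewer, and its one-sided error is between 2.51% and 2.84%.
- At the other 28 sizes the pass marks agree. At n = 90 both need 55, with error 2.23%.

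**Effect on power for this criterion**

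Assume normally distributed percentage loss with the planned mean 6.6% and SD 3.9%. The true response rate is then Phi((6.6 - 5)/3.9) = 65.9%. At n = 100, power is 87.3% under the exact bound and 91.1% under the formula.

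**The case against.** The strongest reply is that the operative sections are right. SAP 12.1.1 tests the LS mean difference against 0 and compares the US lower limit with 2%. SAP 12.1.2 names the exact interval and repeats the success criterion in words. SAP 8 and 9.4 confirm a no-difference hypothesis tested two-sided at 5%. Even in 2.3.1 the words before the hypothesis formula and before the responder formula are sound. All of this stands, and it limits the consequence.

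It also rules out some stronger readings:

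- **That the primary test would be run backwards, or that 2.3.1 alone defines US success.** Sections 12.1.1 and 12.1.2 also define the criteria, and correctly.
- **That the trial will exceed its 2.5% level.** An analyst would have to prefer the gloss to the words of the same bullet and to 12.1.2. Even then the gap is one responder, absent at most sizes examined and at 90 per arm, the size used for power. The 2.84% is also the error of the responder criterion alone, not of the joint US rule.
- **That at or above versus exceeds changes the exact-bound decision.** A lower limit of exactly 50% would need a binomial tail of exactly 1/40. At a rate of 0.5 the tail is an integer divided by 2^n, which can never equal 1/40.
- **That the significance null should be one-sided, muA - muC <= 0.** Protocol 18.1 contains no such null, and it would conflict with the two-sided test in protocol 18.2 and SAP 9.4 and 12.1.1.

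The use of sample means in place of population parameters is a matter of notation, and 2.3.2 does the same throughout.

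The objection does not make the formulas in 2.3.1 correct. They remain part of the stated success rule.

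**Conclusion.** The point holds as an internal contradiction in SAP 2.3.1. The primary null has the wrong inequality, the 2% expression states the alternative, and the responder formula is not the lower limit of the interval the SAP uses.

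The measurable part is small: one responder at 100 active subjects (60 against 61). Wherever the pass marks differ between 80 and 120, the formula is the lenient one and its error is above 2.5%. These figures assume subtraction in the formula, the exact interval of 12.1.2 and, for the headline example, exactly 100 active ITT subjects.

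It should be corrected because it sits in the success rule for a co-primary criterion. The documents do not show that the analysis would be run wrongly.

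**What to change.** In SAP 2.3.1, in population parameters:

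- Both pathways: H0: muA - muC = 0, two-sided.
- USA margin: H0: muA - muC <= 2%, rejected when the lower 95% limit is above 2%. The EU condition on the observed difference can stay as it is.
- USA responders: H0: piA <= 50%. Delete the half-width formula and require the exact (Clopper-Pearson) lower 95% limit to be above 50%, as in 12.1.2.

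The cost is SAP wording only; the data, sample size and analyses in 12.1.1 and 12.1.2 are unchanged. The change should be dated before unblinding. If that point has passed, a documented clarification that 12.1.1 and 12.1.2 govern would remove the ambiguity.

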# Neurovalens Limited Identifier: EXP18020

Clinical Study Identifier: 243973

For the purpose of the *EU regulatory clearance pathway*, the study will be deemed to have met the efficacy criteria if the hypothesis is rejected, and the following numerical criterion is achieved:

• The difference between the mean percentage weight loss of participants using the VeSTAL device and the sham control is at least 2% as observed from the mean estimates.

### 2.3.2 Support Labeling Claims

The secondary endpoints detailed in Section 2.2.2.1 will be used to support labeling claims and will be tested at the 6 month time point in a sequential order after the primary endpoints. These endpoints will assess the difference between treatment groups by considering the change from baseline to the 6 month time point using a linear model.

The first secondary endpoint that will be tested at 6 months is VAT. An increase in VAT loss, as measured by the whole body DXA scan, will be considered successful if significance is declared with the following statistical hypothesis:

• There is no significant difference between the mean percentage VAT loss of participants using the VeSTAL device and the sham control, i.e.  $\bar{x}_v - \bar{x}_s = 0$ , where  $\bar{x}_v$  and  $\bar{x}_s$  are the mean percentage VAT loss of participants using the VeSTAL device and sham control respectively.

The second secondary endpoint to be tested is LDL. A decrease in LDL will be considered successful if significance is declared with the following statistical hypothesis:

• There is no significant difference between the mean percentage change from baseline in LDL of participants using the VeSTAL device and the sham control, i.e.  $\bar{x}_v - \bar{x}_s = 0$ , where  $\bar{x}_v$  and  $\bar{x}_s$  are the mean percentage change from baseline in LDL of participants using the VeSTAL device and sham control respectively.

The third secondary endpoint to be tested is fat loss. An increase in fat loss, as determined by the whole body DXA scan, will be considered successful if significance is declared with the following statistical hypothesis:

• There is no significant difference between the mean percentage fat loss of participants using the VeSTAL device and the sham control, i.e.  $\bar{x}_v - \bar{x}_s = 0$ , where  $\bar{x}_v$  and  $\bar{x}_s$  are the mean percentage fat loss of participants using the VeSTAL device and sham control respectively.

The fourth secondary endpoint to be tested is lean muscle mass. An increase in lean muscle mass, as determined by the whole body DXA scan, will be considered successful if significance is declared with the following statistical hypothesis:

• There is no significant difference between the mean percentage change in lean muscle mass of participants using the VeSTAL device and the sham control, i.e.  $\bar{x}_v - \bar{x}_s = 0$ , where  $\bar{x}_v$  and  $\bar{x}_s$  are the mean percentage change in lean muscle mass of participants using the VeSTAL device and sham control respectively.

Identifier: EXP18020 Clinical Study Identifier: 243973

The fifth secondary endpoint to be tested is the atherogenic index. A decrease in the atherogenic index, as determined by the ratio of total cholesterol to HDL, will be considered successful if significance is declared with the following statistical hypothesis:

• There is no significant difference between the mean change from baseline for the ratio of total cholesterol to HDL of participants using the VeSTAL device and the sham control, i.e.  $\bar{x}_v - \bar{x}_s = 0$ , where  $\bar{x}_v$  and  $\bar{x}_s$  are the mean change from baseline in the ratio of total cholesterol to HDL of participants using the VeSTAL device and sham control respectively.

The sixth secondary endpoint to be tested is systemic inflammation. A decrease in systemic inflammation, as measured by high-sensitivity C-reactive protein, will be considered successful if significance is declared with the following statistical hypothesis:

• There is no significant difference between the mean change from baseline for the high-sensitivity C-reactive protein of participants using the VeSTAL device and the sham control, i.e.  $\bar{x}_v - \bar{x}_s = 0$ , where  $\bar{x}_v$  and  $\bar{x}_s$  are the mean change from baseline in the high-sensitivity C-reactive protein of participants using the VeSTAL device and sham control respectively.

The seventh secondary endpoint that will be tested at 6 months is total calorie intake. A decrease in total calorie intake, as measured by the two-day 24-hour dietary recall, will be considered successful if significance is declared with the following statistical hypothesis:

• There is no significant difference between the mean change from baseline for the total calorie intake of participants using the VeSTAL device and the sham control, i.e.  $\bar{x}_v - \bar{x}_s = 0$ , where  $\bar{x}_v$  and  $\bar{x}_s$  are the mean change from baseline of the total calorie intake of participants using the VeSTAL device and sham control respectively.

The eighth secondary endpoint that will be used to support labeling claims at 6 months is quality of life. An increase in quality of life, as determined using the IWQoL questionnaire, will be considered successful if significance is declared with the following statistical hypothesis:

• There is no significant difference between the mean change from baseline for the total QOL score of participants using the VeSTAL device and the sham control, i.e.  $\bar{x}_v - \bar{x}_s = 0$ , where  $\bar{x}_v$  and  $\bar{x}_s$  are the mean change from baseline in total QOL scores of participants using the VeSTAL device and sham control respectively.

### 3. STUDY DESIGN

The study is designed as a randomized double-blind sham controlled clinical trial to evaluate the efficacy and safety of vestibular nerve stimulation (VeNS), combined with a lifestyle modification program, compared to a sham control and lifestyle modification program, as a means of reducing excess weight.

#### **Neurovalens Limited**

Clinical Study Identifier: 243973

Identifier: EXP18020

The study will be randomized using a parallel assignment with a 1:1 allocation between the active VeSTAL device and the sham control. A total of 200 subjects are planned to be recruited across study sites, with a dropout allowance of 10% to generate a minimum of 90 active treatment and 90 control subjects. The anticipated recruitment across the sites are as follows:

- University of San Diego (UCSD) Altman Clinical and Translational Research Institute (ACTRI): a total of 106 subjects who pass through screening and are randomized.
- UCSD Exercise and Physical Activity Resource Center (EPARC; second trial site at UCSD campus): a total of 100 subjects who pass throughs screening and are randomized.
- University of Ulster (UU): a total of 94 subjects who pass through screening and are randomized.
- Texas Diabetes and Endocrinology (TDE): a total of 40 subjects who pass through screening and are randomized.

Data will be collated from all sites and analyzed as one dataset at the 6-month timepoint. The study is planned to last approximately 6 months for each subject, with the subjects given the headset device to use daily in the home environment.

#### 4. PLANNED ANALYSES

The final analyses will be performed after the study database has been cleaned, locked and the true treatment allocations have been unblinded. Furthermore all randomized subjects will have received their device for a sufficient amount of time to allow 6 month data to be recorded and therefore contribute sufficient data for analysis.

The analyses will commence by summarizing the subject disposition, in particular, reporting the number of subjects in the analysis populations and any subjects that withdrew prior to study reporting or completion. The subject population will be described further by summarizing the demographic and baseline characteristics of subjects.

The efficacy analyses will proceed to investigate primarily any between group differences in the percentage weight loss from baseline adjusting for gender and baseline weight. Further analyses will investigate differences in the primary efficacy endpoints between groups, without adjusting for baseline covariates, repeated measures over time and a binary assessment of weight responders with fat loss >=5%. Multiple imputation will be the primary method for missing data, with LOCF and BOCF as sensitivity methods. The secondary endpoints VAT, LDL, fat loss, lean muscle mass, atherogenic index, sytemmic inflammation, total calorie intake and total QoL score will be analysed sequentially to form the basis of labeling claims.

Other remaining secondary endpoints will be summarised and analysed.

The safety of subjects will be summarized and descriptively compared between groups. The safety data will include a variety of endpoints including adverse events, hearing loss assessments, laboratory measurements, vital signs, and AE questionnaire responses.

The tolerability of device treatment will again be summarized and descriptively compared between groups for treatment exposure (or usage), adherence, and mentor support group usage.

